7.6 Phase I – Determination of Maximum Tolerated Dose (MTD)

7.61 Dose Escalation

Lenalidomide			
Dose Level	Dose	Day	Route
-2	10 mg	Daily for 10 days	Orally
-1	10 mg	Daily for 14 days	Orally
*1	15 mg	Daily for 14 days	Orally
2	20 mg	Daily for 14 days	Orally

***starting dose level**

7.612 Three patients will be treated at each dose level and observed for a minimum of 21 days (1 cycle), to assess toxicities, before new patients are treated. Doses will not be escalated in any individual patient.

7.613 Investigators are to contact the ACCRU Operations Office [contact]) as soon as any dose-limiting toxicity (DLT) occurs.

7.62 Definitions of DLT

7.621 For this protocol, DLT will be defined as an adverse event attributed (definitely, probably, or possibly related) to the study treatment and meeting the following criteria with the first cycle:

- Any grade ≥ 3 non-hematologic adverse event. The following are some of the exceptions noted:
 - Alopecia, anorexia, or fatigue.
 - Grade 3 nausea and/or vomiting if not requiring tube feeding or total parenteral nutrition TPN, or diarrhea if not requiring or prolonging hospitalization that can be managed to Grade ≤ 2 with antiemetic or antidiarrheal medications

- Grade 3 fever with neutropenia, with or without infection.
 - Grade 3 infection.
 - Grade 3 tumor lysis syndrome that resolves within 72 hours after initiation of treatment.
 - Any grade electrolyte alteration that resolves to grade ≤ 1 within 72 hours after it occurs.
- Hematological adverse events include the following:
 - Failure of platelet recovery to 50,000/mm³ by day 29
 - Failure of absolute neutrophil recovery to 1000/mm³ by Day 29

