- 15.47 **Known potential adverse events:** Consult the package insert for the most current and complete information. Percentages reported with single-agent therapy. **Note:** Myelosuppression is dose related, schedule related, and infusion-rate dependent (increased incidences with higher doses, more frequent doses, and longer infusion times) and, in general, rapidly reversible upon discontinuation.
- Common known potential toxicities, > 10%:**
 Central nervous system: Pain
 Endocrine & metabolic: Hyponatremia, hypomagnesemia, hypocalcemia, hypokalemia
 Gastrointestinal: Vomiting, abdominal pain, nausea
 Hematologic: Myelosuppression (dose related and dose limiting; nadir at ~21 days; recovery by ~28 days), leukopenia, anemia, neutropenia, thrombocytopenia
 Hepatic: Alkaline phosphatase increased, AST increased
 Hypersensitivity: Hypersensitivity
 Neuromuscular & skeletal: Weakness
 Renal: Creatinine clearance decreased, BUN increased
- Less common known potential toxicities, 1% - 10%:**
 Central nervous system: Peripheral neuropathy, neurotoxicity

Dermatologic: Alopecia
Gastrointestinal: Constipation, diarrhea, stomatitis/mucositis, taste dysgeusia
Hematologic: Hemorrhagic/bleeding complications
Hepatic: Bilirubin increased
Infection: Infection
Local: Pain at the injection site
Neuromuscular & skeletal: Peripheral neuropathy
Ocular: Visual disturbance
Otic: Ototoxicity
Renal: Creatinine increased

Rare known potential toxicities, <1% (Limited to important or life-threatening):

Anaphylaxis, anorexia, bronchospasm, cardiac failure, cerebrovascular accident, dehydration, embolism, erythema, febrile neutropenia, hemolytic anemia (acute), hemolytic uremic syndrome, hyper-/hypotension, injection site reaction (pain, redness, swelling), limb ischemia (acute), malaise, metastases, pruritus, skin rash, tissue necrosis (associated with extravasation), urticaria, vision loss

15.48 **Drug procurement:** Commercial supplies. Pharmacies or clinics shall obtain supplies from normal commercial supply chain or wholesaler.

15.49 **Nursing guidelines:**

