15.491 Monitor CBC and PLTs. Watch for profound neutropenia and give low count precautions and instructions as necessary. Nadir occurs at approximately day 21 with recovery at day 28-30. Thrombo-neutro-leukopenia may be cumulative. Thrombocytopenia can be dose-limiting and is more pronounced than with cisplatin. It can be more severe in patients with previous chemotherapy, concurrent radiation therapy, or patients with impaired renal function. Instruct patient to immediately report any unusual bruising or bleeding. Anemia (70-90% of patients) may be symptomatic with asthenia being the most common complaint. Instruct patient in energy saving lifestyle.

15.492 Assess baseline renal function (creatinine clearance). Reduced renal function can contribute to an increased risk of thrombocytopenia.

15.493 Monitor fluid status - encourage hydration.

15.494 Advise patient of probable taste alterations. Frequent oral hygiene is helpful. Instruct patient in appropriate interventions to achieve and maintain optimal nutritional status.

15.495 Older patients (>65) may experience some peripheral neuropathy with paresthesias. Instruct patients to report any tingling, burning, loss of sensation.

- 15.496 Mild nausea and vomiting occur in up to 94% of patients, 6-12 hours after treatment and may persist for 24 hours or longer. Diarrhea/cramping/constipation has been experienced by approximately 17%. Premedicate with antiemetics/antidiarrheals—evaluate effectiveness.
- 15.497 Administer following Taxol (in regimens that contain both drugs) to maximize cell kill.
- 15.498 Patients have experienced allergic reactions while receiving carboplatin. Watch for signs and symptoms of hypersensitivity reactions. If these occur, stop drug immediately, notify MD, and treat appropriately.

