The anticipated accrual rate is 4-5 evaluable patients per month. It is anticipated that it will likely take about 2 months to enroll, treat, and evaluate each set of 3 patients in the phase I portion of this study. The phase I portion is expected to take between 6 and 8 months. Once the phase II portion of the trial begins, we can expect to accrue the required patients in about 10-12 months. We can expect to begin final analysis approximately 1.25 years after beginning the phase II portion, i.e. as soon as the last patient accrued has completed the response evaluation after two cycles of treatment and data entry has been completed. The overall study duration is expected to be a maximum of 2 years.

Phase I Portion

16.2 Study Design: The phase I study is designed to determine the maximally tolerated dose (MTD) and toxicity profile of the addition of lenalidomide to R-ICE in patients with first-relapse or primary refractory diffuse large B-cell lymphoma using the standard cohort 3+3 design. Three patients will be treated at each dose level and observed for a minimum of three weeks (i.e. one full cycle) before new patients are treated. Doses will not be escalated in any individual patient.

16.21 MTD Definition: MTD is defined as the dose level below the lowest dose that induces dose-limiting toxicity (DLT) in at least one-third of patients (at least 2 of a maximum of 6 new patients). A total of 6 patients treated at the MTD will be sufficient to identify common toxicities at the MTD. For instance, those toxicities with an incidence of at least 25% will be observed with a probability of at least 82% ($1-(1-0.25)^6$).

Refer to Section 7.62 for definition of dose-limiting toxicity (DLT).

16.22 MTD Determination:

Dose Escalation: The phase I portion of this study will utilize a standard cohort of three design. The dose levels to which patients will be assigned in sequential

cohorts are described in Section 7.61. The first cohort of three patients will be treated at dose level 1. Decisions on when and how to dose escalate are described below.

- 16.221 Three patients will be treated at a given dose level combination and observed for one cycle (3 weeks) to assess toxicity.

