- 16.222 If DLT is not seen in any of the 3 patients, 3 new patients will be accrued and treated at the next higher dose level. If DLT is seen in 2 or 3 of 3 patients treated at a given dose level, then the next 3 patients will be treated at the next lower dose level, if only 3 patients were enrolled and treated at this lower dose level.
- 16.223 If DLT is seen in 1 of 3 patients treated at a given dose level, up to 3 additional patients will be enrolled and treated at the same dose level. If DLT is seen in at least one of these additional three patients (≥ 2 of 6), the MTD will have been exceeded and further accrual will cease to this cohort. If dose-limiting toxicity (DLT) is not seen in any of the three additional patients, 3 new patients will be accrued and treated at the next higher dose level.
- 16.224 After enrolling 6 patients on a specific dose level, if DLT is observed in at least 2 of 6 patients, then the MTD will have been exceeded and defined as the previous dose unless only 3 patients were treated at the lower dose level. In that case, 3 additional patients will be treated at this lower dose level such that a total of 6 patients are treated at the MTD to more fully assess the toxicities associated with the MTD.
- 16.225 Dose de-escalation: If dose-limiting toxicity meets the stopping boundaries set by the above dose escalation algorithm at dose level 1 (for example, more than 1 out of 3 patients or more than 1 out of 6 patients), the next cohort of three patients will be entered at a dose level of -1. If dose level -1 meets the stopping boundaries, the next cohort of three patients will be entered at dose level -2. Further dose re-escalation will depend on the toxicity profile observed at these dose levels, and re-evaluation of the regimen by the study team may be done.
- 16.226 If a patient fails to complete the first cycle of treatment for reasons other than toxicity, the patient will be regarded as inevaluable and will be replaced.

16.227 Operating Characteristics for standard cohort of 3 design: The following table gives the probability of dose escalation at a single dose level as a function of the true probability of DLT at that level using the cohorts of 3 design described above.

True Rate of DLT (%)	Probability of Dose Escalation
10	0.91
20	0.71
30	0.49
40	0.31
50	0.17

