16.45 Data & Safety Monitoring

- 16.451 The principal investigator(s) and the study statistician will review the study at least every quarter to identify accrual, adverse event, and any endpoint problems that might be developing. The Mayo Clinic Cancer Center (MCCC) Data Safety Monitoring Board (DSMB) is responsible for reviewing accrual and safety data for this trial at least twice a year, based on reports provided by the MCCC Statistical Office.
- 16.452 **Adverse Event Stopping Rule:** The stopping rules specified below are based on the knowledge available at study development. We note that the rule may be adjusted in the event of either (1) the study re-opening to accrual or (2) at any time during the conduct of the trial and in consideration of newly acquired information regarding the adverse event profile of the treatments under investigation. The study team may choose to suspend accrual because of unexpected adverse event profiles that have not crossed the specified rule below.

Accrual will be temporarily suspended if at any time we observe events considered at least possibly related to study treatment (i.e. an adverse event with attribute specified as "possible," "probable," or "definite") that satisfy any of the following:

Phase I (Includes all dose levels in phase I): By the nature of the "cohorts of three" phase I study design, toxicity (i.e., adverse events that are possibly, probably or definitely related to study treatment) stopping

rules are in place for each dose level. Specifically, if 2 or more dose-limiting toxicities (DLTs) are observed during cycle 1 at any given dose level, accrual to that dose level will be stopped, and patients will be accrued to the next lower dose level until a maximum of 6 patients are treated at the lower level. Note that a DLT that affects dose escalation is only that which is observed in the first cycle of treatment. However, all cycles will be reviewed and the study team will determine whether the dose level needs to be adjusted for future patients if ≥ 1 in the first 3 patients OR ≥ 2 in the first 6 patients experience a grade 4 or higher non-hematologic adverse event at least possibly related to treatment over all cycles at any given dose level

Phase II (includes all phase II patients, including Phase I patients treated at the MTD):

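### Blood-count DLTs are judged at day 29, but the cohort rules let 20 mg open after 21 days with no instruction to wait for unrecovered counts

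*Combined protocol and SAP*

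**What the plan says.** Section 7.621 lists two hematologic DLTs. One is "Failure of platelet recovery to 50,000/mm³ by day 29"; the other is the matching criterion for neutrophils, ANC to 1000/mm³ by day 29. The section also confines DLTs to the first cycle, and Table 8.1 gives a cycle length of 21 days for all cycles.

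The cohort timing rules all use 21 days:

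- Section 7.612: patients are "observed for a minimum of 21 days (1 cycle), to assess toxicities, before new patients are treated".
- Section 16.2: patients are "observed for a minimum of three weeks (i.e. one full cycle) before new patients are treated".
- Section 16.221, which has no word for a minimum: "Three patients will be treated at a given dose level combination and observed for one cycle (3 weeks) to assess toxicity".

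Section 16.222 then gives the escalation rule: "If DLT is not seen in any of the 3 patients, 3 new patients will be accrued and treated" at the next higher level. Section 16.452 adds: "Note that a DLT that affects dose escalation is only that which is observed in the first cycle of treatment".

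The carboplatin drug information describes the time course of myelosuppression. Section 15.47 has "nadir at ~21 days; recovery by ~28 days" and Section 15.491 has "Nadir occurs at approximately day 21 with recovery at day 28-30". Carboplatin is given on day 2 of the cycle.

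**The concern.** A patient below either threshold on day 21 is neither a DLT nor clear of one, and stays that way for up to eight more days. The earliest permitted cohort decision falls inside that interval. On the protocol's own account of carboplatin, it also falls close to the expected nadir, so an open case is foreseeable. Platelets are the main worry, because growth factor is mandatory and should reduce late neutrophil failures.

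Two things follow. First, a team that follows Sections 16.221 and 16.222 as written can start patients on 20 mg before a DLT at 15 mg can be declared. Second, if the first cycle is read literally as 21 days, a day-29 failure might never enter the escalation count. The review of all cycles in Section 16.452 would not catch it, since that covers only grade 4 or higher non-hematologic events. Section 8.2 holds the affected patient's own next cycle but says nothing about the next cohort.

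The Section 16.227 operating characteristics assume every DLT is known when the decision is made. If the 21-day rule is used, they understate the chance of escalation.

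**Working it through.** **Reproducing the plan's table.** With p the true DLT rate and all DLTs visible, P(escalate) = (1−p)³ + 3p(1−p)² × (1−p)³. For p = 0.10, 0.20, 0.30, 0.40, 0.50 this gives 0.906, 0.709, 0.494, 0.309, 0.172, matching Section 16.227 (0.91, 0.71, 0.49, 0.31, 0.17).

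**Who is still open at day 21.** Section 16.13 expects 4-5 patients per month, so 30.4/4 = 7.6 to 30.4/5 = 6.1 days between patients. With even spacing, when the third patient reaches day 21 the second is at about day 27-29 and the first at about day 33-36. The third is the one clearly short of day 29, so only that patient is modelled as incompletely observed.

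**Assumption.** A share f of DLTs is late hematologic and invisible at day 21. The documents give no value; f = 0.25, 0.50 and 0.75 are used.

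**Formulas.** Let q = p(1−f) be the third patient's visible rate.

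- None of three seen: n0 = (1−p)²(1−q).
- One of three seen: n1 = 2p(1−p)(1−q) + (1−p)²q.
- One of three seen and no late DLT in the third patient: n1* = 2p(1−p)² + (1−p)²q.
- (A) Late DLTs never counted: P(escalate) = n0 + n1 × n0.
- (B) A late DLT in the first three is counted by the six-patient decision: P(escalate) = n0 + n1* × n0.
- (C) 20 mg opens with a 15 mg DLT undeclared, under rule B: (1−p)² × pf × (1 + n1*).

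Worked case, p = 0.30 and f = 0.50: q = 0.15; n0 = 0.49 × 0.85 = 0.4165; n1 = 0.357 + 0.0735 = 0.4305; n1* = 0.294 + 0.0735 = 0.3675. Then A = 0.4165 × 1.4305 = 0.596, B = 0.4165 × 1.3675 = 0.570, and C = 0.49 × 0.15 × 1.3675 = 0.101.

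| True DLT rate | Quantity | f = 0.25 | f = 0.50 | f = 0.75 | Section 16.227 |
|---|---|---|---|---|---|
| 30% | A | 0.545 | 0.596 | 0.646 | 0.49 |
| 30% | B | 0.533 | 0.570 | 0.603 | 0.49 |
| 30% | C | 0.052 | 0.101 | 0.147 | – |
| 40% | A | 0.364 | 0.419 | 0.476 | 0.31 |
| 40% | B | 0.352 | 0.392 | 0.429 | 0.31 |
| 40% | C | 0.050 | 0.098 | 0.143 | – |

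If instead all three patients were judged at day 21, replacing p by q throughout gives 0.65-0.94 at 30% and 0.49-0.91 at 40%. The table above is the more conservative case.

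**Exposure.** The gap is 29 − 21 = 8 days. At the planned accrual that is 8/7.6 = 1.05 to 8/6.1 = 1.3 patients, given that a case is open. Multiplying by C at 30% gives an expected 0.052 × 1.05 = 0.05 to 0.147 × 1.3 = 0.19 patients starting 20 mg with a 15 mg DLT undeclared.

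**Selected MTD.** Assume a 40% DLT rate at both doses and full observation at 20 mg. P(at most 1 of 6) = 0.6⁶ + 6 × 0.4 × 0.6⁵ = 0.233. With no gap, P(declare 20 mg) = 0.309 × 0.233 = 0.072. If two or more DLTs at 15 mg, late ones included, bar 20 mg, it is [n0 + n1*(1−p)³] × 0.233 = 0.079, 0.085, 0.092 for the three values of f. If a single late DLT also triggers the Section 16.223 expansion, it returns to 0.072.

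**The case against.** The strongest reply is that the text permits early escalation without prescribing it. Sections 7.612 and 16.2 set a minimum, and Section 7.612 gives toxicity assessment as its purpose, so the day-29 criterion can be read as part of that assessment. Sites must call the registration office for a dose level before discussing entry. Section 16.13 budgets about two months per cohort; on the spacing above, the third patient reaches day 29 about 41-44 days after the first patient starts, well inside that. Low counts at day 21 would show on the twice-weekly CBC and would hold that patient's own cycle 2. The team would therefore have to escalate with the open case in plain sight.

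On size, the late share has no source in the documents, and the carboplatin text is general drug information. Section 1.2 reports that the earlier trial of lenalidomide with R-ICE gave 25 mg on days 1-7 without dose modifications, though for half the duration planned here. At a 10% DLT rate, rule A gives only 0.92-0.94 against 0.91. The figure of about one patient holds only when a case is open, and it ignores the delay between registration and first dose, which Section 6.36 allows to reach 14 days. Finally, counting a day-29 failure as a first-cycle DLT is the only reading that gives Section 7.621 effect.

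Most of this stands as a reason to expect the problem seldom, and the last point makes outright loss of a late DLT the less likely reading. None of it supplies the missing rule. A minimum allows a wait without requiring one, Section 16.221 omits the word, the registration office has no written instruction to hold, and two months is a forecast.

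**Conclusion.** The concern holds and should be fixed. The mismatch between a day-29 criterion and a 21-day decision rule is in the text and depends on no assumption. Following the stated rules can open 20 mg before a 15 mg DLT can be declared.

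The numerical size is conditional on the assumed 25-75% late share and on one open patient per cohort. On that basis the chance of escalation rises by about 0.04 to 0.17 over the tabulated value at DLT rates of 30-40%, and 20 mg opens over an undeclared DLT with probability 0.05-0.15. The scope is limited to the single planned upward step from 15 to 20 mg. Patients whose counts have recovered by day 21 are already clear on these criteria. The consequence is mainly avoidable exposure at the higher dose. Provided late DLTs are still counted under Sections 16.21 and 16.223, the MTD selected changes little or not at all.

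**What to change.** In Sections 7.621 and 16.452, state that the first-cycle DLT window extends through day 29 for the two count-recovery criteria. In Sections 7.612, 16.2 and 16.221, state that no cohort decision is made until every patient in the cohort has completed 21 days and either has counts recovered to the Section 7.621 thresholds or has reached day 29. With that rule the Section 16.227 table applies as printed.

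The cost is wording in five places. The added wait is at most about 8 days per cohort, only when a patient is unrecovered at day 21, and fits within the roughly two months per cohort already planned. No extra tests are needed, because the test schedule already requires a CBC twice weekly until hematologic recovery or as clinically indicated.

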8.0 Dosage Modification Based on Adverse Events

Dose adjustments of ICE chemotherapy are to be performed per institutional standards. All patients will receive prophylactic hematopoietic growth factors (e.g., granulocyte-colony stimulating factor [G-CSF]) to shorten the period of neutropenia and transfusions of blood products should be provided during the course of treatment per institutional guidelines.

Standard practice and local prescribing information will be followed for rituximab and background chemotherapy. Omitting or discontinuing background therapy must lead to omitting or discontinuing of lenalidomide as well.

Dose Modifications at the start of next treatment cycles:

Dose modifications of Lenalidomide will be based on the dose levels as noted in Table 8.1 and on adverse events noted during preceding cycles (see Table 8.2 for guidance regarding dose reductions based on adverse events).

Dose modifications during a treatment cycle:

Please note, while patient is actively on Lenalidomide, modifications are not allowed during the particular treatment cycle and are only allowed Day 1 of any particular cycle. Decreasing by one dose level would be for the next cycle of treatment. During active treatment cycle, treatment can be held for up to 7 days if needed.

If multiple adverse events are seen, administer dose based on greatest reduction required for any single adverse event observed. Reductions apply to treatment given in the preceding cycle and are based on adverse events observed since the prior dose.

ALERT: ADR reporting may be required for some adverse events (See Section 10)

8.1 Dose Levels (Based on Adverse Events in Table 8.2)

Lenalidomide*				
	Starting Dose 20 mg days 1-14	Starting Dose 15 mg days 1-14	Starting Dose 10 mg days 1-14	Starting Dose 10 mg days 1-10
1 st dose reduction	15 mg days 1-14	10 mg days 1-14	10 mg days 1-10	10 mg Daily for days 1-7
2 nd dose reduction	10 mg days 1-14	10 mg days 1-10	10 mg Daily for days 1-7	Discontinue
3 rd dose reduction	10 mg days 1-10	10 mg Daily for days 1-7	Discontinue	
4 th dose reduction	10 mg Daily for days 1-7	Discontinue		
5 th dose reduction	Discontinue			

* Cycle length is 21 days for all treatment cycles

8.2 Dose modifications for Lenalidomide

Use the following definitions to determine actions in the Action columns of the following tables:

- **Omit** = The current dose(s) for the specified drug(s) during a cycle is skipped. The patient does not make up the omitted dose(s) at a later time
- **Hold/Delay** = The current dose(s) of all drugs during a cycle is delayed. The patient does make up the delayed dose(s) when the patient meets the protocol criteria to restart drugs.
- **Discontinue** = The specified drug(s) are totally stopped.

TREATMENT MODIFICATIONS FOR LENALIDOMIDE Use the NCI Common Terminology Criteria for Adverse Events (CTCAE) version 4.0* unless otherwise specified		
CTCAE System/Organ/Class (SOC)	ADVERSE EVENT	ACTION
BASED ON INTERVAL ADVERSE EVENT DURING TREATMENT (DAYS 2-21)		
Any grade ≥ 3 non-hematologic adverse event	Non-hematologic	No dose reductions allowed while patient is actively getting treatment. Can omit lenalidomide for up to 7 days if needed.
Any grade hematologic adverse event		Does not require dose reduction or omission of Lenalidomide.
AT TIME OF RETREATMENT (DAY 1)		
Investigations/ Neutrophil count decreased	Grade ≥ 3	Hold treatment until ANC ≥ 1000 : 
 • Days 22-28: if ANC ≥ 1000 proceed with treatment without dose reductions. • Days 29-35: If ANC recovers to ≥ 1000, reduce Lenalidomide by one dose level (see Table 8.1). • Days ≥ 36: discontinue treatment and go to event monitoring.
Investigations/ Platelet count decrease	Grade ≥ 3	Hold treatment until platelets $\geq 50,000$: 
 • Days 22-28, if platelets $\geq 50,000$ proceed with treatment without dose reductions. • Days 29-35: If platelets $\geq 50,000$, reduce Lenalidomide by one dose level (see Table 8.1). • Days ≥ 36, discontinue treatment and go to event monitoring.
Any grade ≥ 3 non-hematologic adverse event	Non-hematologic	Need to recover to grade 2 or lower before proceeding. Dose reductions of lenalidomide for the next cycle would be based on Table 8.1

* Located at [REDACTED]

NOTE: If the patient experiences a significant adverse event requiring a dose reduction at the start of the next cycle, then the dose will remain lowered for that entire subsequent cycle. Dose increments would not be allowed once the reductions are made for subsequent cycles.

